## 6.6 Dose modifications for Gastrointestinal Adverse Events

Diarrhea/Colitis	Management/Next Dose of Nivolumab± Ipilimumab
≤ Grade 1	Continue protocol therapy
Grade 2	For Part A and B (Nivolumab alone), may observe and treat symptomatically for 7 days. If persists > 7d, then off protocol therapy. For Parts C, D, and E any grade 2 diarrhea/colitis results in discontinuation of protocol therapy.
Grade 3	Off protocol therapy

Diarrhea/ Colitis	Management/Next Dose of Nivolumab± Ipilimumab
Grade 4	Off protocol therapy
Patients who require steroids should be taken off study treatment. Please evaluate pituitary function prior to starting steroids if possible without compromising acute care. Evaluation for all patients for additional causes includes C. diff, acute and self-limited infectious and foodborne illness, ischemic bowel, diverticulitis, and IBD.	
Recommended management: see GI AE management Algorithm below	

Other GI N-V	Management/Next Dose of Nivolumab ± Ipilimumab
≤ Grade 1	No change in dose.
Grade 2	Hold pending evaluation for gastritis duodenitis and other immune adverse events or other causes. Resume at same dose level if resolution to ≤ Grade 1 within 7 days.
Grade 3	Hold pending evaluation until ≤ Grade 1. Resume at same dose level. If symptoms do not resolve within 7 days with symptomatic treatment patients should go off protocol therapy
Grade 4	Off protocol therapy
Patients with grade 2 or 3 N-V should be evaluated for upper GI inflammation and other immune related events.	

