A cycle may be repeated every 28 days for Parts A and B (and either every 21 days or 28 days for Parts C, D, and E) if the patient has again met the parameters as defined in the eligibility section, [Section 4.0](#), has not met any of the criteria for removal from therapy per [Section 10.1](#), and has not experienced a dose-limiting toxicity. A delay of up to 7 days from the date of the next scheduled treatment dose may be allowed. Please note the following exceptions:

- Patients may continue on to the next cycle if Pancreatic Function is  $\leq$  Grade 1 (See [Section 6.5](#))
- Patients who experience pleural effusion may continue onto the next cycle upon resolution as per [Section 6.8](#).

5.3 **Grading of Adverse Events**

Adverse events (toxicities) will be graded according to the NCI Common Terminology Criteria for Adverse Events (CTCAE) version 5.0. All appropriate treatment areas should have access to a copy of the CTCAE version 5.0. A copy of the CTCAE version 5.0 can be downloaded from the CTEP web site [http://ctep.cancer.gov/protocolDevelopment/electronic\\_applications/ctc.htm](http://ctep.cancer.gov/protocolDevelopment/electronic_applications/ctc.htm). Any suspected or confirmed dose-limiting toxicity should be reported immediately (within 24 hours) to the Study Chair.

5.4 **Definition of Dose-Limiting Toxicity (DLT)**

DLT will be defined as any of the following events that are possibly, probably, or definitely attributable to protocol therapy. DLT definitions will be the same for all parts. The DLT

observation period for the purposes of dose-escalation in Part C or dose de-escalation in Part A will be the first cycle of therapy. Toxicities with subsequent cycles will be monitored carefully and if significant numbers of delayed toxicities are observed, consideration will be given to a protocol amendment to focus on delayed toxicities in assessing the MTD.

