#### 5.4.1 Non-Hematological DLT:

- Any Grade 3 or Grade 4 non-hematological toxicity attributable to protocol therapy with the specific exclusion of:
  - a. Grade 3 ALT that returns to levels that meet initial eligibility criteria or baseline within 7 days and does not require systemic immunosuppression. **Note:** For the purposes of this study the ULN for ALT is defined as 45 U/L. Adverse event grades will be based on increases above the upper limit of normal, regardless of the subject's baseline. See [Appendix IX](#) for toxicity grading table.
  - b. Grade 3 liver enzyme elevation, including AST/SGT that returns to baseline within 7 days and does not require systemic immunosuppression.
  - c. Grade 3 or 4 serum electrolyte or mineral abnormalities responsive to supplementation.
  - d. Grade 3 or 4 amylase or lipase abnormalities that are not associated with diabetes mellitus (DM), associated liver or gall bladder inflammation clinical manifestations of pancreatitis and which decrease to  $\leq$  Grade 2 within 7 days.
  - e. Grade 3 rash/oral lesions that resolves to Grade  $\leq$  1 within 7 days
  - f. Fever greater than 40°C of  $\leq$  24 hr duration
  - g. Grade 3 fatigue that resolves to Grade  $\leq$  2 within 7 days
  - h. Grade 3 creatinine increased that resolves to Grade  $\leq$  1 or baseline within 7 days
  - i. Grade 3 pleural effusion that resolves per [Section 6.8](#)
- Grade 2 fever that does not resolve to Grade  $\leq$  1 within 7 days
- Grade 2 uveitis, eye pain, or blurred vision that does not respond to topical therapy and does not improve to Grade 1 prior to next scheduled dose
- Grade 2 non-hematological toxicity requiring systemic immunosuppressive therapy, including but not limited to, autoimmunity of the lung, heart, kidney, bowel, CNS, pituitary or eye, with the specific exclusion of:
  - a. Grade 2 pleural effusion that resolves per [Section 6.8](#)
  - b. Drugs will be held for grade 2 cardiac dysfunction pending evaluation.
- Grade 2 endocrine toxicity requiring hormone replacement, with the exception of Grade 2 hypothyroidism, thyroiditis and thyroid dysfunction adequately managed with thyroid hormone replacement (see [Section 6.11](#))
- Grade 2 adrenal insufficiency
- Parts A and B: Grade 2 colitis or Grade 2 diarrhea attributable to protocol therapy that persists for  $>$  7 days will be considered a DLT.

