### 6.2 Dose Modifications for Non-Hematological Toxicity

Patients who have any dose-limiting non-hematological toxicity as defined in [Section 5.4.1](#) will be removed from protocol therapy, except as outlined in Sections 6.3-6.12 below.

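### For attributable Grade 3 nausea or vomiting that clears within 7 days, Section 5.2 bars the next cycle while Sections 6.2 and 6.6 allow dosing to resume

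*Combined protocol and SAP*

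**What the plan says.** **Section 6.6 (Other GI N-V, Grade 3).** The row first requires a hold until the event is Grade 1 or less, and continues "Resume at same dose level. If symptoms do not resolve within 7 days with symptomatic treatment patients should go off protocol therapy". It mentions neither attribution nor DLT status.

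**Sections 5.4 and 5.4.1.** A DLT must be "possibly, probably, or definitely attributable to protocol therapy", and "DLT definitions will be the same for all parts". The non-hematological definition opens "Any Grade 3 or Grade 4 non-hematological toxicity attributable to protocol therapy with the specific exclusion of" and lists items a to i: ALT, other liver enzymes, electrolytes, amylase/lipase, rash and oral lesions, fever, fatigue, creatinine and pleural effusion. Nausea and vomiting are absent.

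**Section 5.2.** A cycle may be repeated if, among other conditions, the patient meets the eligibility parameters again "and has not experienced a dose-limiting toxicity". Two exceptions follow, for pancreatic function and pleural effusion.

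**Section 6.2.** Patients with a non-hematological DLT "will be removed from protocol therapy, except as outlined in Sections 6.3-6.12 below". Section 6.6 lies within that range.

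**Section 5.1.5.** In Part E Cycles 1 to 4, both agents are given on Day 1 of a 21-day cycle, with no other dosing day.

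**Section 11.7.1.** Part E closes as too toxic on one Cycle 1 DLT among the first 10 patients, or on 4 patients with DLT among 20.

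**The concern.** A site treating a child whose Grade 3 vomiting settles within a week finds two instructions for the next dose. The toxicity table says to resume, and the criteria for subsequent cycles say the child may not start another cycle. Similar children could be handled differently at different sites, and either course could be recorded as a deviation from some part of the protocol.

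The drafting of neighbouring rows adds to the doubt. Grade 3 fatigue is also hold-and-resume in Section 6.9, and Section 5.4.1 has a matching exclusion: "Grade 3 fatigue that resolves to Grade $\leq$ 2 within 7 days". Rash in Section 6.4 is matched by exclusion e. The Grade 3 liver and pancreatic rows in Section 6.5 refer directly to the exceptions in 5.4.1. The nausea/vomiting row has neither a matching exclusion nor a cross-reference, so a reader cannot tell whether the gap is deliberate. The list matters beyond the individual child, because it also defines the events counted in Section 11.7.1.

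**Working it through.** **Test case.** A child in Part E has Grade 3 vomiting in Cycle 1. It is judged at least possibly related to treatment and returns to Grade 1 or less within 7 days.

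| Question | Section | Answer |
|---|---|---|
| Is it a DLT? | 5.4, 5.4.1 | Yes: attributable, Grade 3, not in a to i |
| Must the child leave therapy? | 6.2 with 6.6 | No: 6.6 outlines resumption |
| May the next cycle start? | 5.2 | No: a DLT has occurred and neither exception applies |
| May the next dose be given? | 6.6 | Yes, at the same dose level |

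**Can the last two answers coexist?** Only if a dose can be given without starting a cycle. In Parts A and B a cycle has doses on Days 1 and 15, so a Day 15 dose could be resumed inside the current cycle. In Part E Cycles 1 to 4 the only dose is on Day 1, so giving it is the same act as starting the cycle. The instructions are then incompatible.

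**Does timing settle it?** No. Section 5.2 tolerates a delay of up to 7 days, and Section 5.4.1 makes a delay of more than 7 days for non-hematological toxicity a DLT. An episode resolving within 7 days can satisfy both and still be a DLT by grade.

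**Does Section 10.1 settle it?** No. Its adverse-event criterion points to Sections 5.4 and 6.0 together without ranking them.

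**Does the conflict reach the closure rule?** First, the plan's own figures, with p the true Cycle 1 DLT rate:

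- First 10 patients: S1 = 1 − (1 − p)^10.
- Overall: S1 + (1 − S1) × P(X ≥ 4 | n = 10, p). After a clean first 10, all 4 patients with DLT must fall in the second 10.

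| p | First 10 | Overall | Plan states |
|---|---|---|---|
| 0.05 | 0.4013 | 0.4019 | 40% overall |
| 0.10 | 0.6513 | 0.6558 | 66% overall |
| 0.20 | 0.8926 | 0.9056 | at least 89% in stage 1, at least 90% overall |

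All four stated figures reproduce. A threshold of 2 DLTs in the first 10 would give 8.6%, 26.4% and 62.4%, which does not match, so the one-event threshold is what was calculated.

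The only input to this rule is the number of patients with a Cycle 1 DLT, and DLT is defined in Sections 5.4 and 5.4.1. Section 6.6 does not enter. The test case therefore adds one to the count whether or not the child is dosed again.

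**The case against.** The strongest reply is that Section 6.2 already resolves the matter. Its exception for Sections 6.3 to 6.12 has content only if some events are both DLTs and resumable. Rash and fatigue that resolve within the stated limits are not DLTs and do not need it, so leaving nausea and vomiting out of the exclusions fits that structure. The footnote to the experimental design schema also speaks of DLTs that require removal, which suggests that not every DLT does. Nor is the gap unique: Section 6.8 lets therapy proceed after managed Grade 3 ascites, while exclusion i covers only pleural effusion.

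Much of this stands. On removal from therapy, Sections 6.2 and 6.6 agree, and the absence of nausea and vomiting from 5.4.1 does not prove an omission. Episodes judged unrelated to treatment are not DLTs and raise no conflict with the DLT condition in Section 5.2. But Section 6.2 governs removal. It does not amend Section 5.2, which sets its own condition, lists its own two exceptions and does not refer to 6.2. The contradiction over starting the next cycle remains.

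A reader might go further and infer that whether one brief episode closes Part E depends on which page the site follows. The documents do not support this. DLT status comes from 5.4/5.4.1 alone. Continuing one patient and closing a cohort are decisions at different levels and do not contradict each other.

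**Conclusion.** The point holds as an internal inconsistency about re-dosing. For Grade 3 nausea or vomiting that is at least possibly attributable and resolves within 7 days, Section 5.2 forbids the next cycle, and Sections 6.2 and 6.6 permit the dose that would start it. Parts A to D are marked completed, so Part E is where it still acts.

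Its size is whether an affected child is dosed again. How often this would arise cannot be stated: the documents list nausea as likely (over 20%) with ipilimumab, but give no rate for short, attributable Grade 3 episodes in Cycle 1.

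No change in closure probability follows. One could assume a 1%, 2% or 5% rate of such episodes on top of a 5% rate of other DLTs, and find the overall chance of closing Part E rising from 40.2% to 46.0%, 51.2% or 64.6%. That compares two different DLT definitions at an assumed rate; it does not measure the conflict between 5.2 and 6.6. As written, the event counts. One such Cycle 1 event among the first 10 patients closes Part E; after a clean first 10, closure needs 4 patients with DLT.

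The conclusion rests on a literal reading of Section 5.2 and on the Part E Day 1 schedule.

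**What to change.** Amend the protocol so that Sections 5.2, 5.4.1, 6.2 and 6.6 give one answer to whether a patient with attributable Grade 3 nausea or vomiting that resolves within 7 days may start the next cycle. In particular, make clear how the exception in Section 6.2 relates to the condition in Section 5.2. In the same amendment, confirm that the exclusion list in 5.4.1 is as intended, since it determines the events counted in Section 11.7.1. Check Grade 3 ascites in Section 6.8 for the same pattern. Which rule applies is for the clinical team to decide.

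The cost is a line or two of text, with no added procedures.

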6.6.1 BMS Recommended Gastrointestinal Adverse Event Management Algorithm

These suggested management guidelines are taken from the BMS algorithms provided in the Investigator’s Brochure.

Opiates/narcotics may mask symptoms of perforation. Infliximab should not be used in cases of perforation or sepsis.

Toxicity (CTCAE v.5)	Management	Follow-up
Grade 1 Diarrhea or Colitis	
 
Continue protocol therapy
 
Symptomatic treatment
 
	
 
Close monitoring for worsening symptoms
 
Educate patient to report worsening immediately
 
 
If worsens:
 
 
Treat as Grade 2 or 3/4
 

Grade 2 Diarrhea or Colitis	
 
Part A or B (Nivolumab alone) symptomatic management. If persists for > 7 days, discontinue protocol therapy.
 
Part C, D, or E discontinue protocol therapy Symptomatic treatment
 
	
If persists > 5-7 days or recurs:
 
 
0.5-1 mg/kg/day methylprednisolone or oral equivalent
 
When symptoms improve to grade 1, taper steroids over at least 1 month
 
Consider prophylactic antibiotics for opportunistic infections
 
 
If worsens or persists > 3-5 days with oral steroids:
 
 
Treat as Grade 3 or 4
 

Toxicity (CTCAE v.5)	Management	Follow-up
Grade 3 or 4 Diarrhea or Colitis	
 
Discontinue protocol therapy
 
1 to 2 mg/kg/day methylprednisolone IV or IV equivalent
 
Add antibiotics for opportunistic infections
 
Consider lower endoscopy
 
	
If improves:
 
 
Continue steroids until grade 1, then taper over at least 1 month
 
 
If persists > 3-5 days or recurs after improvement:
 
 
Add infliximab 5 mg/kg (if no contraindication). Note: Infliximab should not be used in cases of perforation or sepsis
 

Patients on IV steroids may be switched to an equivalent dose of oral corticosteroids (e.g. prednisone) at start of tapering or earlier, once sustained clinical improvement is observed. Lower bioavailability of oral corticosteroids should be taken into account when switching to the equivalent dose of oral corticosteroids.

#### 6.7 Dose Modifications for Pneumonitis

Pneumonitis	Management/Next Dose of Nivolumab ± Ipilimumab
≤ Grade 1	Consider delay in protocol therapy. Resume no change in dose after pulmonary and/or ID consultation
Grade 2	Hold dose pending evaluation and resolution to baseline. Resume no change in dose after pulmonary and/or ID consultation if lymphocytic pneumonitis is excluded.
Grade 3	Off protocol therapy
Grade 4	Off protocol therapy
Distinguishing inflammatory pneumonitis is often a diagnosis of exclusion for patients who do not respond to antibiotics and have no causal organism identified including influenza. Most patients with respiratory failure or hypoxia will be treated with steroids. Bronchoscopy may be required and analysis of lavage fluid for lymphocytic predominance may be helpful. Patients with new lung nodules should be evaluated for sarcoid like granuloma. Please consider recommending seasonal influenza killed vaccine for all patients.	
Recommended management: See Pulmonary Adverse Event Management Algorithm for Pneumonitis below	

##### 6.7.1 BMS Recommended Pulmonary Adverse Event Management Algorithm for Pneumonitis

These suggested management guidelines are taken from the BMS algorithms provided in the Investigator's Brochure.

Evaluate with imaging and pulmonary consultation.

Toxicity (CTCAE v.5)	Management	Follow-up
Grade 1 Pneumonitis	
 
Consider delay of protocol therapy
 
Monitor for symptoms ever 2-3 days
 
Consider Pulmonary and ID consults
 
	
 
Re-image at least every 3 weeks
 
 
If worsens:
 
 
Treat as Grade 2 or 3/4
 

Grade 2 Pneumonitis	
 
Hold infusion
 
Pulmonary and ID consults
 
Monitor symptoms daily, consider hospitalization
 
1 to 2 mg/kg/day methylprednisolone IV or oral equivalent
 
Consider bronchoscopy, lung biopsy
 
	
 
Re-image every 1-3 days
 
 
If improves:
 
 
When symptoms return near baseline, taper steroids over at least 1 month
 
Consider prophylactic antibiotics
 
 
If not improving after 2 weeks or worsening:
 
 
Treat as Grade 3 or 4
 

Grade 3 or 4 Pneumonitis	
 
Discontinue protocol therapy
 
Hospitalize
 
Pulmonary and ID consults
 
2-4 mg/kg/day methylprednisolone IV or IV equivalent
 
Add prophylactic antibiotics for opportunistic infections
 
Consider bronchoscopy, lung biopsy
 
	
If improves to baseline:
 
 
Taper steroids over at least 6 weeks
 
 
If not improving after 48 hours or worsening:
 
 
Add additional immunosuppression (e.g. infliximab, cyclophosphamide, IVIG, or mycophenolate mofetil)
 

Patients on IV steroids may be switched to an equivalent dose of oral corticosteroids (e.g. prednisone) at start of tapering or earlier, once sustained clinical improvement is observed. Lower bioavailability of oral corticosteroids should be taken into account when switching to the equivalent dose of oral corticosteroids.

6.8 **Dose Modification and Adverse Event Management Algorithm for Pleural Effusion and Ascites**

Pleural effusion or ascites	Non-life-threatening (Grade < 4) pleural effusion or ascites	
 
• Treat with appropriate supportive care, which may include: non-investigational diuretics, thoracentesis, chest tube drainage, paracentesis or pleurodesis.
 
• For grade 1 pleural effusion or Grade 1 or 2 ascites, monitor with physical exam and consider additional imaging.
 
• For grade <math>\geq 2</math> pleural effusion or grade 3 ascites, initiate methylprednisolone (2 mg/kg/day IV) or oral equivalent with attempt to taper over 7-10 days after a minimum of 24 hours of treatment.
 
• If chest tube drainage, pleurodesis or paracentesis is required, protocol therapy should be held until at least two days after the procedure or chest tube removal and the patient's condition is stable.
 
• If pleural effusion or ascites resolves or is managed to achieve grade <math>\leq 1</math> and steroids are discontinued, protocol therapy may proceed without dose reduction. If pleural effusion or ascites is not resolved/managed to grade <math>\leq 1</math> and steroids are not discontinued within 28 days of next scheduled dose of nivolumab or ipilimumab, discontinue protocol therapy.
 

	Grade 4 or Life threatening pleural effusion or ascites	
 
• Institute emergency measures per institutional guidelines
 
• Initiate methylprednisolone 2 mg/kg/day IV or oral equivalent with plan to taper as tolerated.
 
• Permanently discontinue protocol therapy
 

### 6.9 Dose Modifications for Fatigue

Fatigue	Management/Next Dose of Nivolumab ± Ipilimumab
≤ Grade 1	No change in dose.
Grade 2	No change in dose
Grade 3	Hold until ≤ Grade 2. If resolves within 7 days, resume at same dose level

Fatigue is the most common adverse event associated with immune checkpoint therapy. Grade 2 or greater fatigue should be evaluated for associated or underlying organ involvement including pituitary, thyroid, and hepatic, or muscle (CPK) inflammation

### 6.10 Dose Modifications for Neurologic Adverse Events

Neurologic events	Management/Next Dose of Nivolumab ± Ipilimumab
≤ Grade 1	Continue protocol therapy*
Grade 2	Hold until resolution to baseline.* Resume with no change in dose.*
Grade 3	Off protocol therapy
Grade 4	Off protocol therapy

\*Patients with any CNS events including aseptic meningitis, encephalitis, symptomatic hypophysitis, or myopathy, peripheral demyelinating neuropathy, cranial neuropathy (other than peripheral n. VII), GB syndrome, myasthenia gravis should be taken off protocol therapy.  
Recommended management: See Neurologic Adverse Event Management Algorithm below

#### 6.10.1 BMS Recommended Neurologic Adverse Event Management Algorithm

These suggested management guidelines are taken from the BMS algorithms provided in the Investigator's Brochure.

Toxicity (CTCAE v.5)	Management	Follow-up
Grade 1 Neurological Toxicity	
 
Continue protocol therapy
 
	
 
Continue to monitor the patient
 
 
If worsens:
 
 
Treat as Grade 2 or 3/4
 

Grade 2* Neurological Toxicity	
 
Hold infusion
 
Treat symptoms per local guidelines
 
Consider 0.5 to 1 mg/kg/day methylprednisolone IV or oral equivalent
 
	
If improves to baseline:
 
 
within 7 days resume protocol therapy, if persists >7 days discontinue protocol therapy
 
 
If worsens:
 
 
Treat as Grade 3/4
 

Toxicity (CTCAE v.5)	Management	Follow-up
Grade 3/4 Neurological Toxicity**	
 
Discontinue protocol therapy
 
Obtain neurology consult
 
Treat symptoms per local guidelines
 
1-2 mg/kg/day methylprednisolone IV or IV equivalent
 
Add prophylactic antibiotics for opportunistic infections
 
	
If improves to Grade 2:
 
 
Taper steroids over at least 1 month
 
 
If worsens or atypical presentation:
 
 
Consider IVIG or other immunosuppressive therapies per local guidelines
 

\* Patients with any CNS events including aseptic meningitis, encephalitis, symptomatic hypophysitis, or myopathy, peripheral demyelinating neuropathy, cranial neuropathy (other than peripheral n. VII), GB syndrome, myasthenia gravis should be taken off protocol therapy.

\*\* With the exception of decreased tendon reflex (DTR); any grade of DTR does not require a dose modification.

Patients on IV steroids may be switched to an equivalent dose of oral corticosteroids (e.g. prednisone) at start of tapering or earlier, once sustained clinical improvement is observed. Lower bioavailability of oral corticosteroids should be taken into account when switching to the equivalent dose of oral corticosteroids.

#### 6.11 Dose Modifications for Endocrine Adverse Events

Endocrine Hypophysitis; Adrenal Insufficiency	Management/Next Dose of Nivolumab ± Ipilimumab
≤ Grade 1	Continue protocol therapy; See Endocrine Management Algorithm
Grade 2	Off protocol therapy if DLT criteria in Section 5.4.1 is met.
Grade 3	Off protocol therapy
Grade 4	Off protocol therapy

Note all patients with symptomatic pituitary enlargement, exclusive of hormone deficiency, but including severe headache or enlarged pituitary on MRI should be considered grade 3 events. Isolated thyroid or testosterone deficiency may be treated as grade 2 if there are no other associated deficiencies and adrenal function is monitored. Please evaluate pituitary function before beginning steroid therapy or replacement therapy of any kind.
	
Recommended management: See Endocrine Management Algorithm	

